8.2 Laboratory Evaluations

To quantitate antibody concentrations elicited by the study vaccines, a baseline blood sample will be collected from all participants at one of the two sites, before the first vaccination and four weeks after the last vaccination.

Preparation, Processing, and Transport of Specimens

Collection of Blood

Following universal precautions, clinicians and experienced nurse/phlebotomists will be trained in appropriate sample collection methods. Appropriate aseptic procedures will be employed with appropriate needles and syringes in place for sample collection procedure. Following universal precautions, a maximum of 2 ml of blood, from a peripheral vein, will be collected by an aseptic technique into serum separator tubes (SST). A maximum of 3 attempts will be made for collection of the blood sample. Sampling attempt will not be repeated in case the team is not able to collect the sample on this day. A blood sample will not be collected for participant who reported a protocol deviation which might have influenced the immune response of the participant as determined by the PI or the medical monitor.

Processing of Blood specimen

Immediately after collection, the blood specimen tube will be gently inverted 4 or 5 times, (labeled with the study participant number, the protocol number and the blood specimen number), and will be stood upright to clot for at least 30 minutes at room temperature before transport to the laboratory at room temperature for processing. The specimen will be transported to the laboratory at PPMC where it will be centrifuged within 8 hours of collection.

Division of Sera

Within 8 hours of collection, clotted blood in the tube will be centrifuged at the PPMC laboratory to obtain serum. Designated laboratory personnel at the site will aliquot the samples into two aliquots as follows:

- \circ 1st aliquot: 0.5 mL for IgA assay
- 2nd aliquot: remaining serum as backup

The study participant number, date and time of collection, blood specimen number, the date and time of division and volume of serum in each aliquot will be specified on a serologic specimen log form/ study worksheet. On this form, comments may be made on the quality of specimens (e.g., hemolyzed, contaminated, etc.).

Conditions for Transport and Storage of Sera

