4.1 Overall Study Design and Plan

The study is designed as a phase III, multicenter, randomized, partially double-blinded, active controlled study enrolling 825 infants 60-91 days of age. The objective of the study is to compare the safety and immunogenicity of the liquid formulation of ROTAVIN with already licensed vaccine ROTAVIN-M1®.

The study will be conducted at commune health centers in Nam Dinh and Quang Ninh provinces in Vietnam. Prospective participants, whose parent or legal guardian sign an informed consent form will be assessed for eligibility to participate in the study. Screening for eligibility will include solicitation of medical history, assessment of vital signs and physical examination. If the participant is found to be eligible, the infants will be allocated to one of the two groups at a ratio of 2:1 to receive the study vaccine with 550 participants receiving the liquid formulation of ROTAVIN and 275 participants receiving the frozen formulation (ROTAVIN-M1®). The study will be conducted according to a partially blinded study design in which the vaccine administrator will be considered unblinded whereas the parents, and rest of the study team including endpoint assessor will be blinded to the treatment received by the child. Two doses of vaccine will be administered 8 (+2) weeks apart (minimum interval of 8 weeks and maximum of 10 weeks), with the first administration given at 60-91 days of age (both days inclusive). Childhood vaccines as per the Expanded Program for Immunization (EPI) of the Government of Vietnam will not be allowed within 7 days before or after study vaccine administration.

To evaluate the Rotavirus vaccine immunogenicity, blood samples will be obtained from all the participating infants from Quang Ninh site before the first vaccination and four (+2) weeks after the second vaccination. Immunogenicity will be assessed in all infants who provided blood samples at the selected site. Serum Anti-rotavirus IgA antibodies will be analyzed at Cincinnati Children's Hospital Medical Center (CCHMC), Cincinnati, Ohio, USA using a validated ELISA which uses strain 89-12 as a substrate.

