7.1 Analysis Populations

Definitions of analysis populations used are:

Enrolled Population: The enrolled population is defined as all screened participants who provide informed consent and are eligible for study participation, regardless of the participant's randomization and treatment status in the study.

Full Analysis (FA) population: The full analysis population is defined as all participants in the enrolled population who were randomized, received the first dose of the study vaccination, and provided at least one evaluable serum sample. The analysis based on this population will serve as supportive results for all immunogenicity objectives.

Participants in the FA population will be analyzed "as randomized", i.e. according to the vaccine a participant was designated to receive, which may be different from the vaccine that the participant actually received.

Per Protocol (PP) population: The per-protocol population is defined as all participants in the FA population who correctly received both study vaccines per randomization with no major protocol deviations that are determined to potentially interfere with the immunogenicity assessment of the study vaccines. This population will serve as the primary analysis population for all immunogenicity objectives. The criteria for exclusion of participants from the PP population is described in Section 10, Table A2, of this SAP.

Safety population: The safety population is defined as all participants in the enrolled population who received at least one dose of study vaccination and had any safety data available.

Participants in the safety population will be analyzed as “treated”, i.e. according to the actual vaccine received at the first dose. All safety analyses will be performed using this population. The denominators for different safety endpoints may vary according to the number of participants with available data for the specific endpoint. For instance, the solicited adverse event endpoints will be based only on those who have the corresponding CRF data regardless of other safety follow-up data.

The immunogenicity primary and secondary endpoints will be performed on the PP and FA population. Safety primary and secondary endpoints will be performed on the safety population. All other baseline and safety analyses, unless stated otherwise, will be performed on the safety population.

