27.	Received Prohibited Medication /Vaccinations / Therapies	Received Licensed Rotavirus vaccine during the study	Administration of any protocol prohibited vaccine including Licensed Rotavirus vaccine (outside of the study centre) during the study period.	No PD review	Exclude
28.	Missed Visit Procedure	Post vaccination assessment missed	Study Procedure related to Medical History / Physical Examination / Vital signs / AE / SAE / 30 mins observation post vaccination is not performed.	No PD review	Include
29.	Missed Visit Procedure	Post-vaccination blood sample missed to be collected from	Post-vaccination blood Sample collection is not performed for immunogenicity	No PD review	Exclude

N	Protocol Deviation Category	Protocol Deviation Subcategory	Detailed Exclusion Description	PD Assessment	Decision for Per Protocol Population
		eligible participant			
30.	Missed Visit Procedure	Assessments (e.g. PE, vitals) at scheduled Visits	Study Procedure related to Medical History / Physical Examination / Vital signs / AE / SAE were not performed at scheduled visits.	No PD review	Include
31.	Deviation to allowable window period	Post vaccination assessment done beyond protocol specified timeline	Study Procedure related to Medical History / Physical Examination / Vital signs / AE / SAE / 30 min observation post vaccination is not performed within specified window period	No PD review	Include
32.	Deviation to allowable window period	Study Procedure Not Performed as per Protocol Visit Schedule	First Dose of vaccine is not administered orally between 60-91 days of life of infant.	No PD review	Exclude
33.	Deviation to allowable window period	Blood sample collected outside specified window period	Blood Sample Collection done after 4 (+2) weeks after last dose of study vaccination	No PD review	Exclude
34.	Deviation to allowable window period	Dose 1 administration beyond 24 hours of randomization	Dose 1 is administration after 24 hours of randomization	No PD review	Include
35.	Deviation to allowable window period	Out of Window Dose 2 Vaccine Administration	Second Dose of vaccine is not administered as per window period (8 +2 weeks from Dose 1)	No PD review	Exclude
36.	Study vaccine administration	Any of the study vaccine dose not administered	Any of the study vaccine dose not administered	No PD review	Exclude

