46.	Immunogenicity result not available	Serological results unavailability	Serological results not available for any of the sampling timepoint (including lost samples, blood sample not done, unable to test, absence of parallelism).	No data review. This exclusion will be filtered at "Analysis Level"	Exclude
47.	Study vaccine administration	Vomiting after repeat dose administration	Subjects who had vomiting/regurgitation within 5 minutes of repeat dose vaccine administration	No data review. This exclusion will be filtered at "Analysis Level"	Exclude

10. Prior and Concomitant Medications

All medications taken since birth are recorded. *Prior medications are defined as those medications taken prior to Day 1 and not continued to be taken on or after Day 1; concomitant medications are defined as those medications continued to be taken or newly initiated on or after Day 1.* All medications will be coded using World Health Organization (WHO) Drug Dictionary.

Prior will be summarized by the anatomical-therapeutic component (ATC) levels 1 and 3 (Table 9). Concomitant medications will be summarized by ATC levels 1 and 3 after any dose and after each dose (Table 10-12). Results will be tabulated for the safety population by the vaccine group and overall. All medications will be listed with concomitant medications separately identified (Listing 8).

Concomitant vaccinations will be summarized by vaccination. Results will be tabulated for the safety population for each vaccine group and overall (Table 13). All EPI vaccinations will be listed (Listing 9).

11. Primary Analyses

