12.1 Immunogenicity

GMC along with the two-sided 95% CI is calculated by exponentiation of the anti-log of the arithmetic mean of the \log_{10} -transformed concentrations. GMC along with the two-sided 95% CI for IgA at baseline and 28 days after the second vaccination will be summarized descriptively by vaccine group for the PP and FA population (Tables 14 and 15, respectively).

Non-inferiority in the immunogenicity of ROTAVIN in comparison to ROTAVIN-M1® is defined as the ratio of GMCs between ROTAVIN and ROTAVIN-M1® is larger than 1/2. The following hypothesis will be tested:

$$H_0: \text{GMC}_{\text{ROTAVIN}}/\text{GMC}_{\text{ROTAVIN-M1}} \leq \frac{1}{2}$$

$$H_1: \text{GMC}_{\text{ROTAVIN}}/\text{GMC}_{\text{ROTAVIN-M1}} > \frac{1}{2}$$

The ratio of GMCs between ROTAVIN and ROTAVIN-M1® along with the two-sided 95% CI is calculated using the log₁₀-transformed anti-rotavirus IgA concentrations to construct a two-sided 95% CI for the mean difference between the two study vaccines using the t-distribution. The mean difference and corresponding 95% CI are exponentiated to obtain the GMC ratio and the corresponding 95% CI. If the lower limit of the 95% CI of the ratio of GMCs between ROTAVIN and ROTAVIN-M1® is larger than 1/2, ROTAVIN is considered to be non-inferior to ROTAVIN-M1®. This results in a one-sided type I error rate of 0.025.

The ratio of the GMCs 28 days after the second dose will be provided along with the two-sided 95% CI for the PP and FA population (Tables 14 and 15, respectively).

The non-inferiority test on the 95% CI for the ratio of GMCs on the PP population is considered the primary analysis. The remaining immunogenicity analyses are considered supportive.

If the serum anti-rotavirus IgA antibody concentration is below the lower limit of quantitation (LLOQ), i.e. assay is recorded as “<LLOQ”, then the concentration will be set to half that limit (LLOQ/2). If the concentration is above the upper limit of quantitation (ULOQ), an actual value will be reported.

An analysis of covariance (ANCOVA) model with the log₁₀-transformed concentrations as the dependent variable, the vaccine group as the explanatory variable, and the log₁₀-transformed baseline concentrations as a covariate will also be performed for the PP and FA population (Tables 14 and 15, respectively). This adjusted analysis will be considered as supportive.

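### Table A2 row 46 drops infants with a valid Day-85 IgA result from the primary analysis when only their baseline result is missing, a small and avoidable loss of precision

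*SAP*

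**What the plan says.** Table A2 (SAP Section 9, Protocol Compliance) lists the grounds for exclusion from PP.

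- Row 46 excludes on this ground: "Serological results not available for any of the sampling timepoint". Its examples include samples that were lost, not taken or could not be tested. No case review takes place; the exclusion is applied as a filter at analysis.
- Row 29 excludes on a narrower ground: "Post-vaccination blood Sample collection is not performed for immunogenicity".
- SAP 4.1 sets two draws at the Quang Ninh site: "before the first vaccination and four (+2) weeks after the second vaccination".
- SAP 7.1 draws PP from the Full Analysis (FA) population, whose members must have "provided at least one evaluable serum sample". One PP population serves every immunogenicity objective.
- SAP 12.1 bases the primary test on log10 IgA 28 days after dose 2, with a 95% CI for the "mean difference between the two study vaccines using the t-distribution", in PP. The ANCOVA with log10 baseline as covariate is labelled supportive.
- Protocol 8.2 allows at most three attempts at a draw and adds: "Sampling attempt will not be repeated in case the team is not able to collect the sample on this day".

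**The concern.** Baseline IgA enters only the supportive ANCOVA, the secondary seroconversion endpoint and the Day 1 descriptive rows. The primary GMC ratio needs the Day-85 value and nothing else. Under row 46, a randomised infant who received both doses correctly and has a valid Day-85 result still leaves the primary analysis if the baseline draw failed or the baseline tube was lost or untestable.

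That sits poorly with the PP definition, which is meant to remove infants whose deviations could interfere with the immunogenicity assessment. A missing pre-dose sample does not change the Day-85 concentration. What is at stake is sample size, and hence the width of the primary confidence interval, together with a primary analysis set that depends on data the primary analysis does not use.

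**Working it through.** **1. What row 46 does.** The wording could mean *missing at either timepoint* or *missing at both*. Under the second reading the row removes nobody, because PP is a subset of FA and FA already requires one evaluable sample. Under the first reading it removes infants lacking a Day-85 result, including lost or untestable samples that row 29 does not reach, and infants lacking only baseline. Only the first reading gives the row any work. Listing 7 also provides for excluded infants whose available results were removed from the immunogenicity analyses.

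**2. The plan's own power figure.** Inputs from Protocol 12.2 and SAP Section 5: 250 vs 125 evaluable, SD 0.8 on the log10 scale, margin 0.5, one-sided alpha 0.025. The true ratio is taken as 1.

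- Distance to the margin: log10(2) = 0.3010
- SE = 0.8 × √(1/250 + 1/125) = 0.0876
- Noncentrality = 0.3010 / 0.0876 = 3.435, with 373 df and critical t 1.966
- Power = 92.9% (noncentral t), against 93% stated. The plan's figure reproduces.

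**3. Power if row 46 removes infants from the 375.** The documents give no rate of baseline-only missingness for this trial. The rates below are assumptions, taken as equal in both arms, with group sizes rounded down.

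| Assumed loss | Group sizes | SE | Noncentrality | Power |
|---|---|---|---|---|
| 0% | 250 vs 125 | 0.0876 | 3.435 | 92.9% |
| 2% | 245 vs 122 | 0.0886 | 3.396 | 92.3% |
| 5% | 237 vs 118 | 0.0901 | 3.340 | 91.5% |
| 10% | 225 vs 112 | 0.0925 | 3.254 | 90.1% |
| 15% | 212 vs 106 | 0.0952 | 3.163 | 88.4% |

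**4. What the documents suggest about the rate.** Protocol 2.5.3 describes the previous ROTAVIN-M1 phase III trial, which drew blood before vaccination and one month after dose 2. It enrolled 800 infants. Table 2.11 shows pre-vaccination results for 600 + 199 = 799, so 1/800 = 0.125% lacked one. Post-vaccination results number 503 + 173 = 676, so (800 − 676)/800 = 15.5% lacked one. Nearly all the loss was at the second draw, which this fix does not recover.

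At 0.125%, the expected loss here is 375 × 0.00125 = 0.5 infant. Removing one infant gives 92.8% power if from the larger arm (249 vs 125) and 92.7% if from the smaller (250 vs 124).

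**5. The allowance.** The 375 is already net of about 15% non-evaluability. With at least 450 enrolled at the site, 450 × 0.85 = 382.5. If infants without a baseline result are counted inside that 15%, the planned 375 and the 93% are kept.

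**The case against.** The strongest defence is that one complete-serology PP set is a deliberate, pre-specified choice. Seroconversion and the ANCOVA need both samples. The Table 14 shell prints Day 1, Day 85, the unadjusted ratio and the adjusted ratio together, so a common set keeps them comparable. Infants dropped by row 46 stay in the FA GMC ratio (Table 15), Table 8 counts exclusions by reason, and Listing 7 flags removed infants who had results. All of this stands and limits the harm. It explains why baseline is required for the baseline-dependent analyses, but not for the primary comparison.

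Three stronger readings are tempting, and the documents do not support them.

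- *Missing baselines will be common.* A reader might infer this from the age range of 60 to 91 days, the three-attempt limit and the no-repeat rule. Those rules give no failure rate, and the one relevant figure in the protocol is about 1 in 800.
- *Rows 29 and 46 contradict each other.* They overlap. Row 29 is silent on baseline and does not direct inclusion of an infant without one; row 46 is the broader ground.
- *The exclusion biases the primary result.* The baseline draw precedes dose 1. Protocol 7.1 assigns non-vaccination procedures to blinded staff, and Protocol 8.2 keeps the laboratory blinded. Nothing ties a missing baseline to the vaccine received.

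**Conclusion.** The point holds as a matter of precision and wording. Row 46 removes valid Day-85 results from the primary PP comparison for lack of a sample that comparison does not use. The likely cost is small: about half an infant and at most about 0.1 power point at the rate in the previous phase III trial, or 0.6 to 1.4 points if 2% to 5% were lost. These figures assume SD 0.8, a true ratio of 1, equal loss in both arms, and losses taken from the 375 rather than absorbed by the 15% allowance. They do not show that the trial is underpowered or that its primary estimate is biased. Priority is low: an optional change, worth making before database lock because it costs little.

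**What to change.** - Reword row 46 as: *Day-85 serological result not available – Exclude*. Keep its existing examples (lost, not taken, untestable) so that they apply to the Day-85 sample.
- State that infants lacking only the baseline result stay in PP for the GMC ratio and Day-85 seropositivity. They are left out of the ANCOVA, seroconversion and the Day 1 rows.
- Change the denominator footnotes of Tables 19 to 22 to participants with the results that each endpoint requires. The Table 19 and 21 footnotes now use the whole PP population, and Tables 20 and 22 follow those shells. Without this change, infants with no baseline would sit in the seroconversion denominator although their status cannot be determined. The FA versions need the correction anyway, because FA requires only one sample.

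The cost is SAP wording and some programming notes. The number analysed will differ slightly between tables; the shells for Tables 14, 19 and 21 already have a row for the number of observations. No change to sampling, enrolment or the primary method is needed.

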12.1 Immunogenicity

GMC along with the two-sided 95% CI is calculated by exponentiation of the anti-log of the arithmetic mean of the \log_{10} -transformed concentrations. GMC along with the two-sided 95% CI for IgA at baseline and 28 days after the second vaccination will be summarized descriptively by vaccine group for the PP and FA population (Tables 14 and 15, respectively).

Non-inferiority in the immunogenicity of ROTAVIN in comparison to ROTAVIN-M1® is defined as the ratio of GMCs between ROTAVIN and ROTAVIN-M1® is larger than 1/2. The following hypothesis will be tested:

$$H_0: \text{GMC}_{\text{ROTAVIN}}/\text{GMC}_{\text{ROTAVIN-M1}} \leq \frac{1}{2}$$

$$H_1: \text{GMC}_{\text{ROTAVIN}}/\text{GMC}_{\text{ROTAVIN-M1}} > \frac{1}{2}$$

The ratio of GMCs between ROTAVIN and ROTAVIN-M1® along with the two-sided 95% CI is calculated using the log₁₀-transformed anti-rotavirus IgA concentrations to construct a two-sided 95% CI for the mean difference between the two study vaccines using the t-distribution. The mean difference and corresponding 95% CI are exponentiated to obtain the GMC ratio and the corresponding 95% CI. If the lower limit of the 95% CI of the ratio of GMCs between ROTAVIN and ROTAVIN-M1® is larger than 1/2, ROTAVIN is considered to be non-inferior to ROTAVIN-M1®. This results in a one-sided type I error rate of 0.025.

The ratio of the GMCs 28 days after the second dose will be provided along with the two-sided 95% CI for the PP and FA population (Tables 14 and 15, respectively).

The non-inferiority test on the 95% CI for the ratio of GMCs on the PP population is considered the primary analysis. The remaining immunogenicity analyses are considered supportive.

If the serum anti-rotavirus IgA antibody concentration is below the lower limit of quantitation (LLOQ), i.e. assay is recorded as “<LLOQ”, then the concentration will be set to half that limit (LLOQ/2). If the concentration is above the upper limit of quantitation (ULOQ), an actual value will be reported.

An analysis of covariance (ANCOVA) model with the log₁₀-transformed concentrations as the dependent variable, the vaccine group as the explanatory variable, and the log₁₀-transformed baseline concentrations as a covariate will also be performed for the PP and FA population (Tables 14 and 15, respectively). This adjusted analysis will be considered as supportive.

ANCOVA Model: $\log_{10}\text{-transformed concentrations} = \beta_0 + \beta_1 \text{Vaccine Group} + \beta_2 \log_{10}\text{-transformed baseline concentrations}$

Immunology data will be listed (Listing 10).

